4.3. Interim Analyses

An interim analysis was not planned for this study.

Statistical Analysis Plan

Sponsor:	Ocular Therape	Ocular Therapeutix, Inc.			
Protocol:	CLN-Protocol-0054				
Document Version No.:	V1.0 Document Date: 01-OCT-2021				

4.4. Subject Disposition

A summary of subject disposition will be tabulated, including the number screened and screened failure, and procedural screen failures will be presented. Subjects are considered procedural screen failures if the investigator is unsuccessful at placing the OTX-CSI or HV intracanalicular ophthalmic insert in both eyes (i.e. neither eye has an insert). The number and percentage of subjects included in each of the analysis populations (ITT, mITT, PP, SAFETY) will be presented by treatment groups and overall. Subject disposition events including randomization, treated, completed study, withdrawal prior to completing the study, and reasons for withdrawal will be summarized by treatment groups and overall.

A by-subject listing of study completion information, including the reason for premature study withdrawal, if applicable, will be presented.

4.5. **Demographic and Baseline Characteristics**

Baseline, demographic and medical history information will be summarized for the mITT and Cohort 1 populations, separately, using descriptive statistics. Demographic characteristic information will include Gender (Male, Female), Age (year), Ethnicity (Hispanic or Latino, Not Hispanic or Latino), and Race (White, Black or African American, Asian, American Indian or Alaska Native, Native Hawaiian or Other Pacific Islander, Unknown, Other).

Demographic and Baseline data will be provided in data listings.

4.5.1. Baseline Ocular Assessments

The following baseline assessments will be presented using descriptive statistics for mITT and Cohort 1 populations, separately, by treatment group and overall.

The assessments below will be presented at the eye level (study eye and non-study eye):

- 1. Unanesthetized Schirmer's Test
- 2. Corneal Fluorescein Staining (tCFS)
- 3. CFS sub-regions using NEI scale
- 4. Conjunctival Lissamine Green Staining (CLGS)
- 5. CLGS sub-regions
- 6. Tear Film Break Up Time (TFBUT)
- 7. Best Corrected Visual Acuity (BCVA) LogMAR Score
- 8. IOP Measurement (mmHg)

Statistical Analysis Plan

Sponsor:	Ocular Therape	Ocular Therapeutix, Inc.		
Protocol:	CLN-Protocol-0054			
Document Version No.:	V1.0 Document Date: 01-OCT-2021			

The assessments below will be presented at the subject level:

- 1. Eye Dryness Severity (VAS) Score
- 2. Eye Dryness Frequency (VAS) Score
- 3. OSDI total score (0-100) and the scores of three domains
- 4. SPEED Total Score (0-28)

4.5.2. Ocular and Non-Ocular Medical History

Medical history, including ocular medical history, will be coded using the MedDRA Version 24.0 - Mar 2021. Non-ocular medical history will be summarized in the mITT and Cohort 1 populations, separately, by system organ class (SOC) and preferred term (PT) by treatment group and overall. SOC will be sorted alphabetically. PT will be sorted by descending frequency overall within each SOC. Subjects with a particular medical history event or medical history class will be counted once at the PT level and once at the SOC level. Ocular medical history will be summarized at the eye and subject levels by treatment group and overall, for the mITT and Cohort 1 populations, separately, with separate summaries for the study eye and non-study eye.

Data listings will be provided for medical history as well.

4.6. **Treatment Exposure**

Details of study drug administration, including duration of treatment will be tabulated and presented in the Safety population. The duration of exposure will be calculated in days as latest date investigator confirms insert is not present in either eye minus date of the earliest insertion in either eye plus 1 and summarized using descriptive statistics by treatment group and overall. Treatment exposure for subjects who discontinue the study prior to the insert no longer being present in both eyes, will be calculated in days as date of last insert visualization in either eye minus date of the earliest insertion in either eye plus 1. In addition, treatment exposure for subjects who discontinue the insert no longer being present in both eyes will be set to the longest observed insert exposure in the applicable cohort as an additional analysis.

All dosing information will be presented in a data listing.

Sponsor:	Ocular Therapeutix, Inc.		
Protocol:	CLN-Protocol-0054		
Document Version No.:	V1.0 Document Date: 01-OCT-2021		

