Once subject eligibility has been determined, OTX-CSI or HV insert, as applicable, will be placed bilaterally, into either the superior or inferior canaliculus (per investigator's preference), during the Insertion/Day 1 (Visit 2) for all subjects who meet the eligibility criteria.

Cohort 1

Subjects in Cohort 1 will undergo Screening 14 days prior to Insertion/Day 1 (Visit 2) to determine eligibility and eligibility will be re-confirmed at Visit 2 (Insertion/Day 1). The treatment follow-up visits will occur at Week 2 (Visit 3), Week 4 (Visit 4), Week 6 (Visit 5), Week 9 (Visit 6), Week 12 (Visit 7), and Week 16 (Visit 8). All subjects in Cohort 1 will be followed until Week 16 (Visit 8) whether or not an insert is visualized.

Cohort 2

Subjects in Cohort 2 will undergo Screening 14 days prior to Insertion/Day 1 (Visit 2) to determine eligibility. At Visit 2 (Insertion/Day 1) eligibility will be confirmed and subjects who are eligible will

be randomly assigned to one of four treatment groups (OTX-CSI Formulation 1, OTX-CSI Formulation 2A, HV Formulation 2B or HV Formulation 3) in a 2:2:2:1 ratio. Should only a unilateral insertion be possible, Visit 2B will occur within 3 days to attempt the insertion again. The treatment follow-up visits will occur at Week 2 (Visit 3), Week 4 (Visit 4), Week 6 (Visit 5), Week 9 (Visit 6), Week 12 (Visit 7), and Week 16 (Visit 8). All subjects in Cohort 2 will be followed until Week 16 (Visit 8) whether or not an insert is visualized.

For both cohorts, if an OTX-CSI or HV insert is visualized in either eye or both eyes at Week 16 (Visit 8) the subject will return to the clinic in 30 days (\pm 10 days; Visit 9) and will continue returning to the clinic every 30 days as needed until an insert can no longer be visualized and the physician has determined that there is no evidence of biological activity. Additionally, subjects may be exited any time at the investigator's discretion. If an OTX-CSI or HV insert cannot be visualized at Week 16 (Visit 8) and the physician has determined that there is no evidence of biological activity, the subject will exit the study.

This study will be conducted per the schedule shown in Figure 1.

Figure 1 Cohort 1 and Cohort 2 Study Schematic

*Subject remains in study until insert is no longer visible and no evidence of biological activity.

Cohort 2

*Subject remains in study until insert is no longer visible and no evidence of biological activity.

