8.3.9 Final Visit 8 (Week 16 ±3 days)

- Record concomitant medications *
- Record AEs *
- Collect and review Subject Daily Diary for Artificial Tear Use (as needed) *
- Urine pregnancy test (WOCBP only)
- VAS for Eye Dryness
- OSDI
- SPEED assessment
- BCVA assessment
- Slit lamp biomicroscopy, including punctum assessment
- OTX-CSI or HV Insert Presence by visual Assessment
- Ease of Visualization by Investigator
- Corneal fluorescein staining (NEI scale)
- Conjunctival Lissamine Green Staining (NEI scale)
- Schirmer Test (without anesthesia) and Tear Film PK

Note: Wait 20 minutes prior to conducting Schirmer/Tear Film PK

- Undilated Fundus Exam (*may be performed before or after IOP)
- IOP
- Punctum Size Assessment
- Dispense artificial tears (as needed)
- Dispense Daily Subject Diary for Artificial Tear Use (as needed)

Note: All ophthalmic assessments must be performed on both eyes.

8.3.10 30-day Follow-Up Visit (Week 20 ± 10 days)

This visit will be conducted every 30 days (\pm 10 days) until an insert can no longer be visualized and the physician has determined that there is no evidence of biological activity.

- Record concomitant medications *
- Record AEs *
- Collect and review Subject Daily Diary for Artificial Tear Use (as needed) *
- VAS for Eye Dryness
- OSDI
- SPEED assessment
- BCVA assessment
- Slit lamp biomicroscopy, including punctum assessment
- OTX-CSI or HV Insert Presence by visual Assessment
- Ease of Visualization by Investigator
- Corneal fluorescein staining (NEI scale)
- Conjunctival Lissamine Green Staining (NEI scale) Schirmer Test (without anesthesia) and Tear Film PK Note: Wait 20 minutes prior to conducting Schirmer/Tear Film PK
- Dispense artificial tears (as needed)
- Dispense Daily Subject Diary for Artificial Tear Use (as needed)

Note: All ophthalmic assessments must be performed on both eyes.

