8.3.11 Replacement of Inserts

For Cohort 1 subjects only, within the first six weeks post treatment, if an insert is not visualized in one or both eyes by the Investigator, the Investigator should place a new insert in the respective eye(s) after confirming patency. Refer to Appendix 13 for placement instructions. Replacement of inserts is not permitted for subjects enrolled in Cohort 2.

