8.3.12 Unscheduled Visit

An unscheduled visit may be performed during the course of the trial in order to ensure subject safety. All procedures performed at an unscheduled visit will be recorded in the source documents and on the Unscheduled Visit eCRF pages.

Evaluations that may be conducted at an Unscheduled Visit may include:

- Slit lamp biomicroscopy
- BCVA assessment
- IOP
- Dilated or Undilated fundus exam
- Urine pregnancy test (if applicable)
- Assessment of AEs
- Assessment of concomitant medications and/or treatments
- Any other assessments needed in the judgment of the investigator

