The two HV insert formulations being studied contain no active drug but differ in their hydrogel formulation. These two formulations are designed to have different hydrogel breakdown periods with one formulation designed to last approximately 1 week (Formulation 3 (F3)) and the other approximately 3 to 4 months (Formulation 2B (F2B)).

Sponsor:	Ocular Therapeutix, Inc.			
Protocol:	CLN-Protocol-0054			
Document Version No.:	V1.0 Document Date: 01-OCT-2021			

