The rest of secondary efficacy endpoint analysis of below parameters will be done similar to analysis of Schirmer test using observed data, for each post-baseline visit (Visit 3, Visit 4, Visit 5, Visit 6, Visit 7, Visit 8, and 30-Day Follow-Up) on mITT and PP populations using observed data:

1. Conjunctival Lissamine Green Staining using NEI scale

2. Ocular Surface Disease Index questionnaire (OSDI©) (total score, each of the three domains and the individual questions)

3. SPEED measures (overall score and individual questions) and its CFB

4.7.4. **Exploratory Analyses**

The exploratory analyses will be done on mITT populations for both study and non-study eye.

The Tear Film Break Up Time at Week 12 and its CFB will be summarized using descriptive statistics (the number of subjects, mean, SD, median, minimum and maximum) by treatment group and overall. Tear Film Break Up Time at Week 12 will be analyzed similar to analysis of Schirmer test using observed data.

Ease of insertion as assessed by the Investigator at Visit 2 or Visit 2B, presence of insert and ease of visualization as assessed by the Investigator at all post-baseline visits will be summarized using discrete statistics (number and percentage) and will be tested between treatment groups (CSI Formulation 1 to HV Formulation 2B, CSI Formulation 2A to HV Formulation 2B, CSI Formulation 1 to HV Formulation 3, CSI Formulation 2A to HV Formulation 3, will be reported. This model will also be used to compare overall OTX-CSI (combined Formulation 1 and Formulation 2A) to each HV Formulation (2B and 3). To analyze ease of insertion as assessed by the Investigator and ease of visualization as assessed by the Investigator, Pearson Chi-squared test will be used. To analyze presence of insert, Fisher's exact Test will be used.

Sponsor:	Ocular Therapeutix, Inc.		
Protocol:	CLN-Protocol-0054		
Document Version No.:	V1.0 Document Date: 01-OCT-2021		

4.8. **Pharmacokinetic Evaluations**

PK analysis will be described separately.

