5. CHANGES TO PLANNED ANALYSES

The language in the SAP will supersede the language in the protocol should there be a discrepancy.

The primary analysis will be repeated for all visits using observed data (without imputation) for both mITT and PP populations. These results will be provided in sensitivity analyses section.

The difference between two OTX-CSI hydrogel formulations as well as the difference between two HV formulations will not be studied. HV formulations will not be combined.

Wilcoxon rank sum test will be used only to analyze LOCF and observed data.

For Eye Dryness Severity and Eye Dryness Frequency, as well total Corneal Fluorescein Staining (tCFS) and its sub-region the main analysis will be based on MCMC MI and sensitivity analyses will be done using LOCF, observed data, and FCS.

For the first secondary efficacy endpoint analysis, for the main analysis, the two groups of change from baseline in Schirmer test (\geq 10 mm vs <10 mm) at visit 7 will be compared between treatment groups using the logistic regression and for the sensitivity analyses, the groups will be compared using LOCF and observed data by Fisher's exact test; Clopper-Pearson method will be used to calculate 95% confidence interval of the proportion of subject with change from baseline in Schirmer Test \geq 10 mm; to calculate 95% confidence interval of the proportion difference, the Chan and Zhang (1999) method will be used.

These analyses will also be performed on all post-baseline visits.

Sponsor:	Ocular Therapeutix, Inc.		
Protocol:	CLN-Protocol-0054		
Document Version No.:	V1.0 Document Date: 01-OCT		01-OCT-2021

6. **REFERENCES**

American Academy of Ophthalmology Cornea/External Disease Panel. Preferred Practice Pattern[®] Guidelines. Dry Eye Syndrome. San Francisco, CA: American Academy of Ophthalmology; 2018. Available at www.aao.org/ppp. Accessed September 23, 2019.

- Disease in the United States Among Adults Aged 18 Years and Older. Am J Ophthalmol. Oct;182:90-98.
- Perry HD. Dry eye disease: Pathophysiology, classification, and diagnosis. Am J Manag Care. 2008;14:S79-S87.
- Schultz C. Safety and efficacy of cyclosporine in the treatment of chronic dry eye. Ophthalmol Eye Dis. 2014;6:37-42.

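### SAP 4.6 ends exposure at the latest confirmed absence of the inserts, so read literally a completer whose inserts went early is credited with about 113 days

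*SAP*

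**What the plan says.** SAP 4.6 (Treatment Exposure) defines duration in days as "latest date investigator confirms insert is not present in either eye minus date of the earliest insertion in either eye plus 1". It is summarised by treatment group and overall in the Safety population (Table 14.1.8). For subjects who leave the study with an insert still in place, the same section ends exposure at the last visualization. It adds an analysis that gives such subjects the longest exposure observed in their cohort. It mentions no removal date.

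Three other provisions decide what the main rule produces:

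- **Presence is checked repeatedly.** Protocol 8.3.4 to 8.3.9 list "OTX-CSI or HV Insert Presence by visual Assessment" at Weeks 2, 4, 6, 9, 12 and 16.
- **Losing the insert does not end follow-up.** Protocol 6.1: "All subjects in Cohort 2 will be followed until Week 16 (Visit 8) whether or not an insert is visualized". The same holds for Cohort 1.
- **Inserts may be removed, and in Cohort 2 they are not replaced.** Protocol 7.6 and SAP 4.2.8 allow removal at the discretion of the investigator or sponsor, and Protocol 10.9.2 requires it on unmasking. Protocol 8.3.11: "Replacement of inserts is not permitted for subjects enrolled in Cohort 2".

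SAP 1.1 gives the intended persistence: about 1 week for Formulation 3, 2 to 3 months for Formulation 1, and 3 to 4 months for Formulations 2A and 2B.

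**The concern.** Absence, once established, is confirmed again at each later visit. The latest date on which it is confirmed is therefore the last visit attended, not the date the insert went. For a completer with no insert at Week 16, the rule as worded measures time in the study rather than time with an insert.

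The exposure table is the SAP's summary of how long subjects carried an insert. If the rule is programmed literally, the overstatement is largest for Formulation 3, the shortest-lived product, and for any insert removed or lost early. The ordering of subjects can also reverse, because early leavers with an insert in place are cut off at last visualization while completers run to Week 16.

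**Working it through.** The documents state no exposure figure, so there is none to reproduce. The check is date arithmetic.

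**Inputs.** The formula is (end date − earliest insertion date) + 1, from SAP 4.6. Scheduled presence checks fall 14, 28, 42, 63, 84 and 112 days after insertion (Protocol 8.3.4 to 8.3.9), taking Week *w* as 7*w* days. Windows are ±2 days at Weeks 2 and 4 and ±3 days from Week 6. Subjects with an insert visible at Week 16 return 30 ± 10 days later, and again as needed (Protocol 6.1).

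**Two readings.** Literal: the end date is the last visit confirming absence in both eyes. First-absence: the end date is the first such visit.

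| First visit with both inserts absent | First-absence reading | Literal reading | Excess (days) |
|---|---|---|---|
| Week 2 | 14 + 1 = 15 | 113 | 98 |
| Week 4 | 28 + 1 = 29 | 113 | 84 |
| Week 6 | 42 + 1 = 43 | 113 | 70 |
| Week 9 | 63 + 1 = 64 | 113 | 49 |
| Week 12 | 84 + 1 = 85 | 113 | 28 |
| Week 16 | 112 + 1 = 113 | 113 | 0 |
| 30 days after Week 16 | 142 + 1 = 143 | 143 | 0 |

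The literal column assumes exit at Week 16, or at the first return visit in the last row. With windows, Week 2 gives 13 to 17 days, Week 9 gives 61 to 67, and Week 16 gives 110 to 116. The first return visit gives 109 + 20 + 1 = 130 to 115 + 40 + 1 = 156.

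**By formulation, if inserts last as intended** (30.4 days per month; absence found at the next scheduled check):

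- Formulation 3, 7 days: first absent at Week 2, so 15 days against 113.
- Formulation 1, 2 months (61 days): first absent at Week 9, so 64 against 113. At 3 months (91 days): first absent at Week 16, so 113 on both readings.
- Formulations 2A and 2B, 3 months: 113 on both readings. At 4 months (122 days): 143 on both.

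**Ordering.** A subject who withdraws with an insert last seen at Week 9 gets 63 + 1 = 64 days. A completer whose inserts were gone by Week 2 gets 113 on the literal reading.

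**Removal date.** Take an illustrative removal of both inserts 21 days after insertion. Dated at removal, exposure is 21 + 1 = 22 days. Dated at the next scheduled check (Week 4), it is 29. On the literal reading it is 113. On the first-absence reading the delay cannot exceed the gap between checks: 14 days up to Week 6, 21 days to Week 12, and 28 days to Week 16. The number of removals is not given. Assuming 1 to 4 late-dated subjects in an arm of 40, each delayed by the full 28 days, the arm mean rises by 28 × 1/40 = 0.7 to 28 × 4/40 = 2.8 days at most.

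**The case against.** The best defence is that the literal reading is not the intended one. The rule pairs a latest date across eyes with the earliest insertion across eyes, which reads naturally as last eye to lose its insert minus first eye inserted. The rest of SAP 4.6 also treats exposure as time with an insert, since early leavers are cut off at last visualization. That is probably what was meant, and it is why the point is minor. But the text never says first, and a programmer following it could produce either column of the table.

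A reader might also draw two stronger conclusions that the documents do not support.

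- **That the exposure table could not tell a 1-week vehicle from a 3 to 4 month insert.** An insert visible at Week 16 is followed until it is gone, which gives about 143 days or more even on the literal reading. Presence is also tabulated by arm and visit (Tables 14.2.4.3.1 and 14.2.4.3.2) and listed by subject (Listing 16.1.14), and a short-lived vehicle would show there.
- **That the presence analysis in SAP 4.7.4 is faulty because it sets no category for removed inserts.** The SAP says "To analyze presence of insert, Fisher's exact Test will be used", and counting a removed insert as not present is correct for simple presence. Only table titles are available, so the table layouts are unknown, and so is the number of removals. Removals for adverse events should appear in Listing 16.1.16.3. SAP section 5 also withdraws the comparisons between the two active formulations and between the two vehicles.

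Nor can it be said that removals would go undated. Protocol 8.3.12 requires procedures at an unscheduled visit to be recorded, and the eCRF is not in the documents. What stands is that SAP 4.6 does not use a removal date.

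**Conclusion.** The concern holds as a minor wording fault. Read literally, SAP 4.6 gives about 113 days (110 to 116) to every completer with no insert seen at Week 16 who exits then. The overstatement is up to 98 days, for inserts gone by Week 2, and falls to nothing for inserts first absent at Week 16 or later. On the probable intended reading, only the missing removal date remains. Its effect on an arm mean is at most 0.7 to 2.8 days under the assumed 1 to 4 removals of 40.

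The figures assume nominal visit dates and, for the formulation examples, inserts that last as intended. If Week 16 is counted as Day 112, 113 becomes 112.

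The consequence is limited to the descriptive exposure table and the additional analysis based on the longest observed exposure. The Schirmer endpoint, the other efficacy analyses and the Fisher tests on presence are untouched.

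**What to change.** Reword the main derivation in SAP 4.6 along these lines:

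> For each eye, exposure ends at the earlier of (a) the date of final insert removal not followed by re-insertion and (b) the first visit at which absence is confirmed with no later visualization or replacement. Subject exposure is the later of the two eyes' end dates minus the date of the earliest insertion in either eye plus 1.

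The condition on re-insertion matters because Protocol Appendix 13 has the investigator remove and replace a badly seated insert at placement; without it such an eye would get one day. The condition on replacement also covers Cohort 1, where lost inserts are replaced in the first six weeks. Keep the existing last-visualization rule for subjects who leave the study with an insert in place.

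The cost is one reworded derivation, using the removal date where it is recorded. No visit, procedure, table or test is added, and the presence analysis stays as planned.

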4.7. Efficacy Evaluation

The efficacy summaries and analyses will be presented for both study and non-study eyes for Cohort 2 only.

The Primary efficacy analysis of the Schirmer test will be conducted using the mITT and PP populations. All the efficacy parameters, with the exception of categorical Schirmer test evaluation (i.e., \geq 10 mm increase in Schirmer) and the categorical BCVA evaluation (i.e. Loss of 3 lines of vision), will be analyzed as continuous variables. Their absolute values at each timepoint (Visit 1, Visit 2, Baseline, Visit 3, Visit 4, Visit 5, Visit 6, Visit 7, Visit 8, and 30-Day Follow-Up), and change from baseline to each post-baseline visit will be summarized using descriptive statistics (the number of subjects, mean, SD, median, minimum and maximum) by treatment group and overall. The number and percentage of subjects with \geq 10 mm increase from baseline in Schirmer test and loss of 3 lines of vision based on BCVA at each post-baseline visit will be tabulated by treatment group and overall. The results for 30-Day Follow-Up visits will be reported only for observed data.

4.7.1. **Primary Analyses**

For the primary efficacy endpoint analyses of Schirmer Test change from baseline, the following modeling and analyses will be performed on MCMC MI of mITT population:

A linear model with fixed effects of treatment (four individual formulations) and baseline Schirmer test value as covariate will be used to compare different formulations in terms of Schirmer Test change from baseline at Visit 7 (Week 12) and all other post-baseline visits (Visit 3, Visit 4, Visit 5, Visit 6, and Visit 8). In the linear model, least square means treatment group comparison of CSI Formulation 1 to HV Formulation 2B, CSI Formulation 2A to HV Formulation 2B, CSI Formulation 1 to HV Formulation 3, CSI Formulation 2A to HV Formulation 3, will be reported. This model will also be used to compare overall OTX-CSI (combined Formulation 1 and Formulation 2A using sample size weights of Formulation 1 and Formulation 2A as coefficients for the parameters in least square means treatment group comparison) to each HV Formulation (2B and 3). Unadjusted treatment group analyses using two-sample t-test will be run on these treatment group combinations.

These analyses will also be performed on the PP population.

Sponsor:	Ocular Therapeutix, Inc.		
Protocol:	CLN-Protocol-0054		
Document Version No.:	V1.0 Document Date:		01-OCT-2021

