approximately 0.36 mg of cyclosporine and is designed to deliver therapeutic levels of cyclosporine onto the ocular surface for a duration of approximately 12 weeks. Continuous release of cyclosporine from the hydrogel inserts may result in higher daily concentrations of cyclosporine delivered to the ocular surface than is found with topical Restasis. In a beagle dog study, the average cyclosporine release rate from OTX-CSI was 3.5 μ g/day, exceeding the estimated daily bioavailable dose from Restasis of <1.4 μ g cyclosporine per day. Tear fluid concentrations of cyclosporine measured in the beagle dog studies were typically 1 to 3 μ g/mL. It is known that cyclosporine accumulates with repeat dosing in the cornea and lacrimal gland in animal studies (Acheampong et al, 1999), and this may be the case with sustained cyclosporine delivery from OTX-CSI. However, considering the low cyclosporine concentrations required at the ocular surface, OTX-CSI, offers promise as a potential sustained release treatment for patients with signs and symptoms of DED for approximately 12 weeks with a single insert.

The two active formulations of OTX-CSI being studied in this clinical trial contain the same cyclosporine dose and release drug at the same daily rates but differ in their hydrogel composition. These two formulations are designed to have different breakdown periods of the hydrogel with one formulation designed to last approximately 2 to 3 months (Formulation 1) and the other approximately 3 to 4 months (Formulation 2A). These formulations have been evaluated in prior human clinical trials conducted by the sponsor either with an active molecule or in a non-significant risk (NSR) study. The difference between these two OTX-CSI hydrogel formulations will be studied for retention and persistence in this Phase 1/2 clinical study.

The two HV insert formulations being studied contain no active drug but differ in their hydrogel formulation. These two formulations are designed to have different hydrogel breakdown periods with one formulation designed to last approximately 1 week (Formulation 3) and the other approximately 3 to 4 months (Formulation 2B). The difference between these two HV formulations will be studied in the clinical study as they provide for a short-acting and long-acting placebo.

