1. INTRODUCTION AND OBJECTIVES OF ANALYSIS

1.1. Introduction

Dry Eye Disease (DED)

Dry eye disease (DED), also known as Keratoconjunctivitis Sicca (KCS), is one of the most common ophthalmic disorders presenting to the clinician (American Academy of Ophthalmology, 2018). Prevalence of dry eye is higher among women than men (Farrand et al, 2017). Prevalence also increases with age with 2.7% of Americans age 18 to 34 years and 18.6% of Americans ≥75 years diagnosed with DED (Farrand et al, 2017).

DED is a multifactorial disorder of the tear film and ocular surface that results in eye discomfort, visual disturbances, tear film instability, and often ocular surface damage (Perry, 2008; Schultz, 2014). In humans, dry eye was found to be associated with the presence of conjunctival T-cells and elevated levels of inflammatory cytokines in the tears compared with controls (Massingale et al, 2009; Lee et al, 2013).

Investigational Product Rationale

In order to address the limitations of topical ophthalmic eye drops, Ocular Therapeutix has developed OTX-CSI (cyclosporine ophthalmic insert) for intracanalicular use. OTX-CSI combines the benefits of cyclosporine with punctal occlusion, an effective therapy for DED (McCabe, 2009). OTX-CSI contains approximately 0.36 mg of cyclosporine and is designed to deliver therapeutic levels of cyclosporine onto the ocular surface for a duration of approximately 12 weeks. Continuous release of cyclosporine from the hydrogel inserts may result in higher daily concentrations of cyclosporine delivered to the ocular surface than is found with topical Restasis.

Considering the low cyclosporine concentrations required at the ocular surface, OTX-CSI, offers promise as a potential sustained release treatment for patients with signs and symptoms of DED for approximately 12 weeks with a single insert.

The two active formulations of OTX-CSI being studied in this clinical trial contain the same cyclosporine dose and release drug at the same daily rates but differ in their hydrogel composition. These two formulations are designed to have different breakdown periods of the hydrogel with one formulation designed to last approximately 2 to 3 months (Formulation 1 (F1)) and the other approximately 3 to 4 months (Formulation 2A (F2A)).

Sponsor:	Ocular Therapeutix, Inc.			
Protocol:	CLN-Protocol-0054			
Document Version No.:	V1.0	Document Date:	01-OCT-2021	

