7.3.5. SAS codes to run ANCOVA (using PROC MIXED) on MI data

ods output LSMESTIMATEs=LSMESTIMATEs; proc mixed data= pr2; by AVISITN IMPUT; CLASS TRPG1N (ref=last); MODEL CHG=TRPG1N base; Ismeans TRPG1N/ cl pdiff; LSMESTIMATE TRPG1N "1G1" **1000**, "2G2" 0 1 0 0, /* WF1 and WF2 are the sample size weighted coefficient for group 1 and 2 respectively*/ "3G(1/2)" &WF1. &WF2A. 00, "4G3" **0010**, "5G4" 0001, "6G1 vs G3" 10-10, "7G2 vs G3" **01-10**, "8G1 vs G4" **100-1**, "91G2 vs G4" 0 1 0 -1, "92G(1/2) vs G3" &WF1. &WF2A. -10, "93G(1/2) vs G4" &WF1. &WF2A. 0-1 / cl;

run;

proc sort data=LSMESTIMATEs; by AVISITN LABEL;

run;

Sponsor:	Ocular Therapeutix, Inc.			
Protocol:	CLN-Protocol-0054			
Document Version No.:	V1.0	Document Date:	01-OCT-2021	

ods output ParameterEstimates=outIsmean; PROC MIANALYZE DATA=LSMESTIMATEs; modeleffects estimate; stderr stderr; by AVISITN LABEL; RUN;

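### Should SAP 4.7.1 name one OTX-CSI v vehicle contrast as the sole basis for a cyclosporine claim?

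*SAP*

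**What the plan says.** SAP 4.7.1 fits a linear model with four treatment levels and baseline Schirmer value. It reports "least square means treatment group comparison of CSI Formulation 1 to HV Formulation 2B, CSI Formulation 2A to HV Formulation 2B", the same two active formulations against HV Formulation 3, and pooled OTX-CSI against each vehicle. SAP 7.3.5 codes the same six contrasts. None is ranked. SAP 4.2.6 declares no alpha adjustment for multiple endpoints.

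The facts that give each contrast its meaning are in SAP 1.1:
- The product is not drug alone: "OTX-CSI combines the benefits of cyclosporine with punctal occlusion, an effective therapy for DED".
- The active inserts are "designed to last approximately 2 to 3 months (Formulation 1 (F1)) and the other approximately 3 to 4 months (Formulation 2A (F2A".
- The vehicles are "designed to last approximately 1 week (Formulation 3 (F3)) and the other approximately 3 to 4 months (Formulation 2B (F2B".

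Protocol 4.2 says of the vehicles: "The difference between these two HV formulations will be studied in the clinical study as they provide for a short-acting and long-acting placebo". SAP section 5 withdraws this, stating that the difference between the two active formulations "as well as the difference between two HV formulations will not be studied", and it also declines to pool the vehicles. SAP 2.2 gives the Cohort 2 objective as safety, tolerability and efficacy of OTX-CSI.

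**The concern.** The choice of vehicle changes the question. Against F3, designed to be gone after about a week, a Week 12 difference contains cyclosporine plus about three months of extra occlusion. Against F2B, designed to last as long as F2A, the F2A difference contains cyclosporine only. F1 lies between, because Week 12 falls inside its breakdown period.

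The awkward result is a split one: an F3 contrast favours OTX-CSI and F2A v F2B does not. The SAP has no sentence on whether a drug effect beyond the insert may then be claimed. It has also dropped the direct F2B v F3 comparison that might have helped. If occlusion alone raises Schirmer scores, an F3 result could be presented as a cyclosporine effect, and an interpretation chosen after unmasking could follow the data. That would argue for fixing F2A v F2B in advance as the only basis for a drug claim and for adding an F2B v F3 output row.

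**Working it through.** **Inputs.** Arms of 40/40/40/20 for F1, F2A, F2B and F3 (SAP 2.1); two-sided alpha 0.05 (SAP 4.2.1); Week 12 ±3 days (SAP Table 1); designed persistence (SAP 1.1). The documents state no SD, power or effect size, so there is no planned figure to reproduce. Results are in SD units, with complete data, no gain from the covariate, 135 df and critical t 1.978.

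**Persistence at Week 12.** The window is day 84 ± 3, that is day 81 to 87. At 30.44 days per month, F1 (2 to 3 months) runs to day 61 to 91, and F2A and F2B (3 to 4 months) to day 91 to 122. F3 ends at about day 7. So F2A and F2B should be present, F1 is within its breakdown window and F3 is gone. The reading of each contrast follows directly from the SAP's own introduction.

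**Standard errors**, SE = √(Σc²/n):
- F1 or F2A v F2B: √(1/40 + 1/40) = 0.224
- F1 or F2A v F3: √(1/40 + 1/20) = 0.274; the same for F2B v F3
- Pooled v F2B: √(0.25/40 + 0.25/40 + 1/40) = 0.194
- Pooled v F3: √(0.25/40 + 0.25/40 + 1/20) = 0.250

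**No drug effect.** Let occlusion be worth *o* SD and let a fraction *p* of F1 inserts be present. Arm means are then F1 = *op*, F2A = *o*, F2B = *o*, F3 = 0. Both *o* and *p* are assumed.

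| *o* (SD) | At least one F3 contrast significantly favours OTX-CSI (*p* = 0 to 1) | Split result: an F3 contrast does, F2A v F2B does not (*p* = 0.5 to 1) |
|---|---|---|
| 0 | 4.4% | not computed |
| 0.1 | 7% to 9% | 7% to 9% |
| 0.25 | 15% to 23% | 16% to 21% |
| 0.5 | 44% to 58% | 45% to 56% |

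When *o* is above 0 these are mostly not false positives: the product does differ from a one-week vehicle.

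**F2B contrasts in the same model.**
- F2A v F2B: *o* − *o* = 0
- F1 v F2B: *op* − *o* = *o*(*p* − 1) ≤ 0
- Pooled v F2B: *o*(*p* − 1)/2 ≤ 0

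Each therefore favours OTX-CSI significantly in at most 2.5% of trials. At *o* = 0.25 and *p* = 0.5, F1 v F2B does so in 0.6% and pooled v F2B in 1.1%. Even if any one of the three were accepted, the chance is at most 3 × 2.5% = 7.5%.

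**Cost of making F2A v F2B the sole basis.** With drug effect *d* in both active arms, F2A v F2B estimates *d*, and pooled v F2B estimates *d* − *o*(1 − *p*)/2. At *d* = 0.5:

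| Case | Pooled difference | Power, pooled v F2B | Power, F2A v F2B |
|---|---|---|---|
| *p* = 1 | 0.5 | 73% | 60% |
| *o* = 0.25, *p* = 0.5 | 0.5 − 0.0625 = 0.4375 | 61% | 60% |
| *o* = 0.5, *p* = 0 | 0.5 − 0.25 = 0.25 | 25% | 60% |

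Neither contrast is better throughout.

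**The F2B v F3 row.** Its 95% half-width is 1.978 × 0.274 = 0.54 SD. The interval lies wholly above 0 in only 5%, 15% and 44% of trials at *o* = 0.1, 0.25 and 0.5. The `cl pdiff` option on the least-squares-means line in SAP 7.3.5 already requests this difference, with a confidence interval, in each completed dataset. Only the pooling step leaves it out. The observed-data and LOCF analyses need no pooling, so it appears there directly if the same model code is used.

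**The case for a change.** The strongest case for a change is that the facts are scattered, that nothing says which contrast answers which question, and that a sentence written before unmasking costs almost nothing and stops the reading from following the result. The split case is not rare if occlusion works: about one trial in six to one in five at 0.25 SD. The SAP also dropped both the pooled-vehicle comparison and the vehicle difference.

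Part of this stands. The contrasts are unlabelled, and an F3 contrast alone does not isolate cyclosporine. But the documents do not define a cyclosporine-alone claim or a success rule that the missing sentence would protect. The distinction they support is between F2B and F3 as comparators. Singling out F2A v F2B goes further: it would bar a claim from a significant pooled v F2B result, although that contrast can only lean against the product under the model above. Not pooling the vehicles keeps the two questions apart. The changes are declared in SAP section 5, as protocol 11.9 allows.

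**Conclusion.** No change to the plan follows. The missing label is a gap that a competent analyst fills from SAP 1.1 and the insert-presence tables (14.2.4.3.1 and 14.2.4.3.2). F3 contrasts describe the whole product, which is the stated objective. A statement about cyclosporine beyond the insert needs support from an F2B contrast. Applied as written, the plan gives valid estimates for both questions. The proposed sole basis exchanges 60% power for anywhere between 25% and 73%, depending on F1 retention and the occlusion effect, so it is a preference between reasonable options. The extra F2B v F3 row would be too imprecise to divide an F3 result between drug and occlusion.

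This rests on assumed occlusion effects of 0 to 0.5 SD, additive drug and occlusion effects, an equal drug effect in both active arms, and persistence close to design. Cohort 2 inserts are not replaced, so if F2A and F2B differ in actual retention, even that contrast is not perfectly matched. This is a further reason to read every contrast with the presence tables.
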